1.1 Summary of the Study

Title: Prevention of infestation with *Pediculus humanus*

capitis in the family group using a pediculicidal shampoo: A prospective, randomised controlled

study.

Chief Investigator: [name]

Study Monitoring: Onorach Limited

Estimated Study Start: January 2022

Estimated Study Finish: March 2022

Participants: Eighty-four (84) participants (the Index Cases) with

evidence of an active head louse infestation and their Households as the unit of randomisation will be recruited

to the study. All Index Cases will be treated with

Vamousse Treatment Mousse. Forty-two (42) participants and their Households will be treated with Vamousse Lice Defence Shampoo and forty-two (42) with The Control Shampoo. All participants will use the randomly assigned shampoo for fourteen (14) days and will be assessed for active head lice infestation at the end of that time.

Type: Eligible children and adults

Products: Vamousse Lice Defence Shampoo and The Control

Shampoo.

Methods of Application:

Both preparations will be applied to wet hair, massaged into the scalp and left in the hair for 3 minutes and no more than 5 minutes before rinsing with water and towel-drying. (see Section 2.3.3.2).

Study Design:

Participants will be recruited into the study by household and randomised to receive either Vamousse Lice Defence Shampoo or The Control Shampoo.

Index cases will be assessed for presence of head lice at their day of recruitment (Day 0) in order to ensure that all participants have live lice present at the start of the study. Other family members who proactively complain of head lice infestation will be treated as though they are an index case. All index cases will be treated the same day with Vamousse Treatment Mousse following confirmation of their eligibility. A member of the Medical Entomology Centre (MEC) study team will apply the treatment. All members of the household will commence using Vamousse Lice Defence Shampoo on Day 0 and will continue to use the shampoo daily for fourteen (14) days.

On Day 3, the index case will be assessed for lice infestation; if necessary, a second treatment with Vamousse Treatment Mousse will be applied. Index cases with active infestation on Day 3 will be assessed again on Day 6 and treated again if the infestation is still active. All participants will be assessed for the presence of live head lice by dry detection combing on Day 14. No other active assessments will take place during the course of the study. If, however, a member of the household complains of infestation, a member of the MEC team will confirm the presence of live lice and they will be offered treatment with Vamousse Treatment Mousse.

Aims of the Study:

To demonstrate superiority of Vamousse Lice Defence Shampoo to The Control Shampoo in the prevention of lice infestation among close family members.

1.2 Rationale

Despite the introduction of physically acting treatments for head louse infestation that are not affected by resistance, infestation with the human head louse (*Pediculus capitis*) is still of widespread concern, partly because most families act individually and there are no coordinated efforts to eliminate infestation in most communities and partly because not all products are fully effective to eliminate infestation.

It has long been known that infestations of head lice occur most frequently in young children, but that the wider family can be a source of spreading the infestation and of re-infestation. Detection combing is a skilled procedure and may not be effective in the hands of the general public and over-use of neurotoxic insecticidal lice treatments has led to the evolution of resistant strains of head lice. The active ingredients in Vamousse Shampoo have been demonstrated in vitro to dissolve the waxy cuticle of the louse, which then dies from dehydration. As the shampoo is less effective at killing lice eggs, the shampoo needs to be used for approximately two weeks, in order that all nymphs, hatching from viable eggs, can be exposed to the shampoo.

The rationale behind this study is that treatment with a cosmetically acceptable, daily use lice-killing shampoo can help to prevent the spread of an infestation among close family members, prevent re-infestation of the index case and therefore reduce the impact of the infestation. To this end, the study will evaluate the superiority of Vamousse Lice Defence Shampoo used daily for 14 days in preventing the spread of infestation in the household, compared to a control shampoo with no active ingredients.

1.3 Aims (Objectives)

- To compare efficacy of Vamousse Lice Defence Shampoo and The Control Shampoo with the aim of demonstrating the superiority of Vamousse Lice Defence Shampoo compared to The Control Shampoo in preventing the spread of infestation in a household.
- 2. To confirm the safety and acceptability in use of Vamousse Lice Defence Shampoo.

1.4 Design in Brief

This trial will be a randomised, parallel group study of a topical treatment for head lice (Vamousse Lice Defence Shampoo) in comparison with a control preparation (The Control Shampoo). At least eighty-four (84) index cases and their households will be recruited, randomised by household and stratified by family size (see Section 3.4 for

details).

At the first visit (Day 0), verbal consent will be obtained to check for the presence of live head lice in the index case, using a fine-toothed plastic detection comb. Any other family member who proactively complains of infestation will also be checked and thereafter will receive treatment as though they are an index case, but will still count as a member of the household. Other household members will not be assessed for the presence of lice.

After the preliminary assessment, participants can be enrolled to the study, provided the index case has an active infestation, all individuals comply with the inclusion/exclusion criteria and any further questions they may have are fully dealt with.

Participants (or their parents/guardians if they are younger than 16 years) will be asked to give written informed consent and sign a Consent Form before participation in the study. There will be a separate Assent Form for children capable of giving written assent. Assent Forms will be witnessed by the parent/guardian and signed by the Investigator.

All prospective index cases who fit the selection criteria (see section 2.1.2 and 2.1.3) will be confirmed as having an active head louse infestation prior to commencement of treatment (see below).

The household of the index cases enrolled on to the study will be randomly allocated to receive one of the two study preparations with at least forty-two (42) individuals allocated to each (see Section 3.4 for details). The Investigator will assign each Initial index case a study number, this being the next available number from a randomised treatment allocation sequence. The treatment allocations will be made double blinded, identified only by a code. Instructions for use will be held in sealed envelopes and will only be opened after consent has been received. Assignment will continue until there are at least forty-two (42) initial index cases in each group.

The population will be stratified according to the following criteria:

Number of children $<3/\ge3$ and number of overt infestations on Day 0 =1/>1.

Index cases will be treated with Vamousse Treatment Mousse at Day 0. A member of the MEC study team will apply the treatment. This treatment is designed to eliminate infestation. Combing to remove lice or louse eggs, in addition to the shampoo treatment, will not be given in this study.

Starting on Day 0 and ending on Day 14, all participants will commence using the shampoo as part of their daily routine. As appropriate, reminders can be issued by SMS text.

The index case will be assessed for active infestation on Day 3 ± 1 . If live lice are present, Vamousse Treatment Mousse will be applied again. Index cases with active infestation on Day 3 will be screened again on Day 6 ± 1 and re-treated if live lice are detected.

On day 14 \pm 1, all participants will be assessed for infestation by dry detection combing. Those with signs of an active infestation will be recorded as treatment failures. Anyone who has a head louse infestation at the end of the study will be provided with the standard of care treatment (Vamousse Treatment Mousse), as will any infested household member who is a non-participant.

It is possible that a participant may complain of infestation during the course of the study, although participants should be discouraged from taking active steps to detect the presence of lice. If this does occur, the individual should contact the MEC study team, who will confirm the presence of live lice and offer treatment. The individual will be recorded as a treatment failure in the CRF.

All adverse events will be monitored during the study (see sections 2.3.5 and 2.3.6) and all changes in concomitant health conditions and/or medication will be recorded (see section 2.3.4). A Completion/Withdrawal Form will be completed at the end of the study period.

2. Materials and Methods

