2.3.3.2 Recruitment (Day 0)

Screening:

Each potential index case will be asked for permission to assess their hair to determine

whether live head lice are present at the start of the study. The assessment will be made by dry combing the hair with a plastic fine-toothed head louse detection comb. Any family member complaining of symptoms of infestation will also be assessed and if confirmed, will be recorded in the CRF. Thereafter, they will receive treatment as though they are an index case. Other family members will not be assessed.

Details will be recorded of how many people share the place of residence with the index case(s).

Consent/Assent:

Potential participants and/or parents/guardians will be asked if they understand the requirements of the study, as set out in the PIB, and if they have any further questions concerning it. Provided they still wish to enter the study and meet the inclusion/exclusion criteria for entry, the participant or parent/guardian (when the participant is below the age of 16) will read and sign the Consent Form. The Investigator will countersign the Consent Form.

A separate Assent Form will be available for those under the age of 16 provided they are capable of signing their name. The Investigator and the parent/guardian will countersign the Assent Forms. A copy of the Consent Form and, if appropriate the Assent Form, will be given to the individual or the carer.

Should an adult member of the household not meet with the inclusion/exclusion criteria, it may not necessarily mean the entire household is ineligible. At the discretion of the investigator, the household may be enrolled and the excluded family member will recorded as a non-participant.

Case Record Form completion:

Personal data allowing identification of an individual will not be recorded in the CRF. However, as there are no source medical documents (i.e. patient medical records) available to the investigators, a Source Data Verification Sheet will be completed for each participant that will be maintained separately from all other study documentation. This Sheet will include information such as name, date of birth, address, and contact details for the General Practitioner. A copy of the GDPR statement covering security of personal data collected during the course of the study will be given to the carer.

The following information will be recorded in the CRF:

- 1. Declaration of Receipt of Informed Consent and GDPR statement:

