3.1.2 Efficacy

The primary outcome of the study is the proportion of individuals in each household with active head lice infestation at day 14.

Secondary objectives are:

To demonstrate the safety of Vamousse Lice Defence Shampoo in clinical use.

To demonstrate the acceptability of Vamousse Lice Defence Shampoo in daily use.

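### The primary endpoint, Day 14 household prevalence, cannot separate prevention of spread from clearance of infestation undetected on Day 0, so the objective and conclusion should be worded for what is measured

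*Protocol*

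**What the plan says.** **Aim.** Section 1.1 states it as "To demonstrate superiority of Vamousse Lice Defence Shampoo to The Control Shampoo in the prevention of lice infestation among close family members". Section 1.3 says "in preventing the spread of infestation in a household", and section 3.4 repeats the idea.

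**Endpoint.** Section 3.1.2: "The primary outcome of the study is the proportion of individuals in each household with active head lice infestation at day 14". Neither this section nor section 3.4 restricts the proportion to people free of lice on Day 0.

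**Baseline examination.** The index case is combed on Day 0, as is any member who complains. For the rest, section 1.4 says "Other household members will not be assessed for the presence of lice" and section 2.3.3.2 says "Other family members will not be assessed". Unless they complain later, Day 14 is their first examination.

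**Confirmed Day 0 cases.** Complaining members found infested "will receive treatment as though they are an index case, but will still count as a member of the household". Of the Mousse, section 1.4 says "This treatment is designed to eliminate infestation". Nothing takes the primary index case out of the proportion.

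**Mechanism.** Section 1.2 presents the shampoo as killing lice. It justifies about two weeks of use by the need to reach nymphs hatching from eggs already present, and it names the wider family as a possible source of spread and re-infestation. It also gives protection of the index case from re-infestation as a purpose.

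**The concern.** Spread means that a person without lice acquires them. For most household members the trial never establishes who was without lice at the start. A member infested at Day 14 may have carried lice since Day 0. A member clear at Day 14 may have been protected, or may have been infested and then cleared by the shampoo. The endpoint scores both kinds of clear member alike.

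The treated Day 0 cases add a second mixture. Their Day 14 status combines failure of the Mousse with re-infestation. The Day 3 and Day 6 checks tell something about which it was, but the endpoint does not use them.

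What is at stake is the claim. A significant primary result would be reported as prevention of spread, although clearance of existing infestation could have produced some or all of it.

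**Working it through.** **1. The plan's own figure.** Section 3.4 gives family rates of 0.7 and 0.4, SD 0.367, values truncated to 0–1, two strata variables (probabilities 0.7 and 0.5) and a two-sided 5% test. It reports 90.56% power at 42 families per arm. Simulating that recipe with a stratified summed-rank Wilcoxon test (10,000 replicates) gives 90.9%. At 30 and 36 per arm it gives 77.7% and 85.6%, against 74.86% and 83.74% stated. The protocol does not set out the exact form of the Fry-Lee test; van Elteren weights give 93.2% at 42. The stated power is reproduced, so the point concerns what the endpoint means and not the sample size arithmetic.

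**2. Illustration with no direct preventive effect.** All inputs in this step are assumptions:
- *p*: silent Day 0 prevalence among the other members, 10% to 50%
- *c*: clearance of silent infestation, 60% with the test shampoo and none with control
- *t*: new infestation, 20% in both arms
- household: one index case, infested at Day 14 with probability 0.20 in both arms, plus three others

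Rate among the other members:
- control = *p* + (1 − *p*)*t*
- test = *p*(1 − *c*) + [1 − *p*(1 − *c*)]*t*

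Household rate = (0.20 + 3 × rate among others) / 4.

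For *p* = 0.5:
- control: 0.5 + 0.5 × 0.2 = 0.60, so the household rate is (0.20 + 1.80)/4 = 0.50
- test: 0.2 + 0.8 × 0.2 = 0.36, so the household rate is (0.20 + 1.08)/4 = 0.32

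The household means then go through the simulation of step 1 at 42 per arm.

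| Silent Day 0 prevalence | Others, control / test | Household, control / test | Trials significant |
|---|---|---|---|
| 10% | 0.280 / 0.232 | 0.260 / 0.224 | about 7% |
| 20% | 0.360 / 0.264 | 0.320 / 0.248 | about 12% |
| 30% | 0.440 / 0.296 | 0.380 / 0.272 | about 22% |
| 50% | 0.600 / 0.360 | 0.500 / 0.320 | about 50% |

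Repeat runs agree to within about 2 percentage points. The first row is barely above the 5% level of the test.

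**3. Weight of the index case.** One index case in four shrinks the difference by a quarter: at *p* = 0.5, 0.24 × 3/4 = 0.18. Leaving the index case out would raise the last row from about 50% to about 75%, but that would not be the protocol's endpoint.

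**4. Sensitivity to the model.** A different model draws whole counts per household (index plus three others, 10% new infestation, index 20% infested in both arms, intra-household correlation 0.2). With 50% clearance, significance runs from about 10% of trials at 10% silent prevalence to between 79% and 90% at 50%. With 80% clearance it runs from a little over 20% to nearly 100%. The result depends heavily on inputs the protocol does not state.

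**The case against.** **The randomised comparison is sound.** Households are randomised, so silent Day 0 infestation balances on average. The Mousse and its Day 3 and Day 6 repeats follow one rule in both arms. A reader might infer that the primary test is biased or its type I error inflated. The documents do not support that: the test is valid for a difference in Day 14 household prevalence.

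**Killing lice on unnoticed carriers may itself reduce spread.** Section 1.2 treats the family as a source of infestation, so clearance is part of the expected mechanism. This stands. Holding new infestation equal in both arms is an artificial extreme, and it would be too strong to say that a significant result has no bearing on the aim. The result still cannot show how much was prevention.

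**Index cases are counted for a reason.** Section 1.2 wants to protect them from re-infestation. A reader might infer that they must leave the primary proportion. That does not follow: the rates of 0.7 and 0.4 and the 42 families per arm are stated for whole families, so a new denominator would change the endpoint and require a new sample size.

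**Stratification and louse staging help.** Only in part. The strata in section 2.3.1 cover overt Day 0 cases. The staging in section 2.3.3.6 is outside the endpoint, and its inference presumes that the infestation was first eliminated. It cannot date adult lice on a head never examined on Day 0.

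**Conclusion.** The point holds as a mismatch between claim and endpoint. The aim is prevention of spread; the endpoint is Day 14 household prevalence with no condition on Day 0 status, under a shampoo that kills existing lice. A valid difference may mean clearance, prevention or both.

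Its size cannot be fixed from the protocol, which gives no silent prevalence, clearance rate, new-infestation rate or household size. Under the main assumptions above, a shampoo with no direct preventive effect reaches significance in about 7% to 50% of trials as silent prevalence goes from 10% to 50%. At low silent prevalence the problem is small.

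A reader might take a single high figure, such as 75% or 95%, as the chance of a false prevention claim. Those values arise only with 50% to 60% silent prevalence and with the index case left out; with one index case added they fall to about 50% and 75%. A reader might also infer that the trial must comb everybody on Day 0. That is an extra procedure which the plan deliberately omits, and the mismatch can be resolved without it.

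**What to change.** 1. Keep the randomised primary comparison and its whole-household denominator, on which the sample size rests.
2. Word the objective and the conclusion as: *reduces the proportion of household members infested at Day 14 (clearance of undetected infestation and/or prevention of new infestation)*. Do not claim prevention of spread from this endpoint alone.
3. Add a supportive analysis of the household proportion among members not confirmed infested on Day 0. State in advance how a household with no such members is handled.
4. Report Day 14 infestation of primary and secondary index cases separately.

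**Cost.** Items 3 and 4 use data the CRF already collects, since section 2.3.3.2 has confirmed Day 0 cases recorded there. No visit, examination or change in sample size is needed. The price is a narrower claim and one more analysis, together with the separate tabulation of index cases. Item 3 removes the known Day 0 cases but not the silent ones, so it supports the reworded conclusion and does not restore the prevention claim.

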3.4 Statistical Methods

Sample size determination

The study has been designed to detect superiority of the test product (Vamousse Lice Defence Shampoo) (the treated group) to the comparator product (The Control Shampoo) (the placebo group) in clinical use.

The primary analysis proposed (see **Analytical Methods** below) is a comparison of the efficacy of the products with the aim to detect for superiority of Vamousse Lice Defence Shampoo to The Control Shampoo in the prevention of spread of infestation in a close household. The primary parameter on which this will be based is the proportion of individuals with active infestation at Day 14 in each household.

Stratifications – 1: <3 children in a household versus ≥ 3 children in a household and 2: overt infestations on Day 0 = 1 Index Case versus > 1 Index Case.

The principal analysis will be a stratified Kruskal-Wallis test using the Fry-Lee Test[1].

Significance will be declared at a level of 5%, using a two-sided test for greater percentage of infected family members in the placebo group versus the treated group.

To work out the numbers required to treat the code for calculating the probability of rejecting using the Fry-Lee Test[1] was put into an R routine, with the results validated against results from the proprietary package RoeLee[2].

From previous studies it was estimated that the infection rate in untreated families would be about 0.7 with standard error 0.367. The treatment is intended to lower the rate by 30%, so the rate in the treated group should be about 0.4 with standard error 0.367.

For a given number of families in each arm a random set of rates was then simulated using these mean and standard errors, using the R routine pnormal, truncating the values so that values less than zero were given the value zero, and values greater than one were given the value one.

The values were then checked to see if they would reject on a two-sided test at the significance level of 5%.

This process was repeated 5000 times and the rate of rejection used to estimate the power of the test.

If the power of the test was less than the required power, in this case 90%, the number of observations was increased and the process repeated.

To deal with stratification, two extra variables were simulated in each run, the first with a probability of being positive set at 0.5, and the second set at 0.7. The result of the test was calculated allowing for these strata.

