Starting from a default value of 30 families per group the following results were found:

Kruskal Wallis Analysis of Data Study Size calculations based upon 5000 replicates

Normal Distribution. Test of Mean2 - Mean1 (Std.Dev. known). 2-sided . Wilcoxon-Mann-Whitney Use Truncated Normal Distribution - x < 0 -> 0, x > 1 -> 1Stratify data, (Fry-Lee Test). Two strata vars, 1:prob of strata level 2 = 0.7 2:prob of strata level 2 = 0.5Sample Size 1 as a function of Power and Significance Level. H0: Mean 2 - Mean 1=0 H1: Mean 1=0.7 H1: Mean 2=0.4 Std.Deviation 1=0.367 Std.Deviation 2=0.367, Sample Size 2 / Sample Size 1=1

Significance Level

| - 9 | | | |
|--------|------------|--------|-------|
| Number | .001 | 0.01 | 0.05 |
| Pov | ver Requir | ed: 90 | |
| 30 | 19.24 | 49.50 | 74.86 |
| 31 | 22.46 | 52.30 | 76.48 |
| 32 | 23.66 | 55.14 | 78.36 |
| 33 | 25.38 | 56.24 | 79.72 |
| 34 | 28.10 | 58.80 | 81.88 |
| 35 | 29.62 | 61.04 | 82.66 |
| 36 | 30.62 | 62.12 | 83.74 |
| 37 | 34.30 | 65.80 | 85.58 |
| 38 | 36.32 | 66.50 | 85.74 |
| 39 | 38.36 | 68.88 | 87.64 |
| 40 | 39.66 | 70.90 | 88.74 |
| 41 | 41.42 | 72.34 | 89.68 |
| 42 | 44.18 | 74.44 | 90.56 |
| | | | |

Thus 42 families per group should be sufficient to give a 90% power to detect a difference at two-sided significance level of 5%. Experience from previous studies of this kind suggests that drop-outs are infrequent. As described in section 3.2, non-compliant households will be included in the ITT analysis with the last observation for drop outs or lost to follow up cases carried forward for analysis. Nevertheless, should any families drop out of the study, recruitment will continue until at least 84 families have completed the study.

References

Analytical methods

Analyses will be conducted based on both the "intention-to-treat" and the "per-protocol" populations and will initially use conventional analytical methods employed in earlier studies. Differences between the groups in baseline characteristics, safety, acceptability, and efficacy will be tested using Fisher's Exact test for yes/no variables and the Mann-Whitney U test for ranked variables. Where analysis shows important differences in baseline characteristics between the groups, Chi-Square and rank tests stratified for these characteristics may also be conducted.

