The primary endpoint, the rate of family members infested at the end of the trial, will be analysed by the stratified Kruskal-Wallis Test (Fry-Lee Test). This will be stratified on family size (<3 children in a household versus ≥3 children in a household) and overt infestations on Day 0 (=1 Index Case versus >1 Index Case). Significance will be declared at a level of 5% on a two-side test of the rate being lower in the treated group versus the placebo group.

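### A confirmed mid-study infestation is a treatment failure in section 1.4, but the primary outcome counts only Day 14 status, so rescue treatment can erase the event

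*Protocol*

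**What the plan says.** **The failure rule (Protocol 1.1 and 1.4).** If a household member complains of infestation during the study, "a member of the MEC team will confirm the presence of live lice and they will be offered treatment with Vamousse Treatment Mousse" (1.1). Section 1.4 adds: "The individual will be recorded as a treatment failure in the CRF". The same section uses the same label for the final combing: "Those with signs of an active infestation will be recorded as treatment failures". Of the Mousse it says: "This treatment is designed to eliminate infestation".

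**The primary outcome (Protocol 3.1.2 and 3.4).** It is defined three times, each time by status at the end:
- 3.1.2: "The primary outcome of the study is the proportion of individuals in each household with active head lice infestation at day 14"
- 3.4, sample size: "The primary parameter on which this will be based is the proportion of individuals with active infestation at Day 14 in each household"
- 3.4, analytical methods: "The primary endpoint, the rate of family members infested at the end of the trial"

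**Related rules.** Section 3.4 keeps non-compliant households in the intention-to-treat analysis, "with the last observation for drop outs or lost to follow up cases carried forward for analysis". Section 3.2 keeps premature terminations, including those for treatment failure, in that population but does not say how they are scored. Section 2.3.7 makes withdrawal for lack of efficacy the participant's choice.

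**The concern.** One label covers two groups, and the primary outcome picks up only one of them. The trial asks whether the shampoo prevents spread within the household (1.3). A confirmed new infestation in a shampoo user is that event. Under the endpoint as written, the event drops out of the household proportion if a treatment that was not randomised, given because of the event, clears it before Day 14.

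Two things are at stake. The first is validity: the between-arm contrast comes to depend partly on who complains and whom the Mousse clears. The second is consistency: two identical confirmed cases can be scored differently according to whether they remain in the study.

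**Working it through.** **1. One household under the two rules.** Take a household of four participants (size chosen for illustration). Two members have live lice confirmed on Day 7 and accept the Mousse; the other two are never infested.
- Failure rule of 1.4: 2/4 = 0.50.
- Day 14 outcome, both stay and are clear: 0/4 = 0.
- Day 14 outcome, one stays and is clear, the other drops out and the last (infested) observation is carried forward: 1/4 = 0.25.

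The same clinical course gives three values. Everyone still in the study is combed at Day 14, so a cleared participant has an observed negative result and carry-forward does not apply.

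**2. The plan's own power figure.** Section 3.4 gives 90.56% at 42 families per group: rates 0.7 and 0.4, SD 0.367, values clipped to 0–1, two strata variables with probabilities 0.7 and 0.5, two-sided 5%. Simulating this with within-stratum rank sums added over strata gives 90.7%, 91.1% and 91.7% in three runs of 5,000. At 36 and 30 per group the same code gives 85.2% and 78.6%, against 83.74% and 74.86% in the protocol. The exact test weighting is therefore only approximated, but the design point agrees and is not in dispute.

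**3. Effect of the Day 14 rule if 0.7 and 0.4 are cumulative rates.** Let s be the share of infested members who report and c the share of those whom the Mousse clears.

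Day 14 rate = cumulative rate × (1 − s × c)

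The protocol gives neither s nor c. Assume c = 0.8 and vary s. For 10% reporting in both arms: 0.7 × (1 − 0.08) = 0.644 and 0.4 × (1 − 0.08) = 0.368, a difference of 0.276 instead of 0.300. Power is simulated with 42 households per arm of 3–6 members, intraclass correlation 0.47 (household SD about 0.355–0.380) and four strata. Ranges show the spread between independent runs.

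| Reporting, control / active | Day 14 rates | Difference | Power |
|---|---|---|---|
| None erased | 0.700 / 0.400 | 0.300 | 91–93% |
| 5% / 5% | 0.672 / 0.384 | 0.288 | about 90% |
| 10% / 10% | 0.644 / 0.368 | 0.276 | about 88% |
| 20% / 20% | 0.588 / 0.336 | 0.252 | 85–87% |
| 30% / 30% | 0.532 / 0.304 | 0.228 | 83–84% |
| 50% / 50% | 0.420 / 0.240 | 0.180 | 75–76% |
| 10% / 5% | 0.644 / 0.384 | 0.260 | about 83% |
| 40% / 20% | 0.476 / 0.336 | 0.140 | 45–47% |
| 20% / 40% | 0.588 / 0.272 | 0.316 | difference exaggerated |

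With equal reporting the difference is 0.300 × (1 − s × c), so it always shrinks. With unequal reporting it can shrink sharply or, as in the last row, exceed the true 0.300.

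**4. Dependence on the model.** In the protocol's clipped-normal model, with the SD held at 0.367, clearing 10%, 20% or 30% of failures in both arms gives 84%, 76% or 64%. These are shares cleared, so 10% corresponds to 0.10 / 0.8 = 12.5% reporting in the table. This model is harsher than the household model, so the loss is not a firm number.

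**5. If 0.7 and 0.4 are already Day 14 rates.** Applying the formula would then discount them twice. The planned power applies to the Day 14 rule unchanged.

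**The case against.** **The endpoint is consistent.** All three definitions agree, and the CRF entry can be read as data capture only. Day 14 status regardless of rescue is a legitimate quantity to estimate. That stands in part: a reader might infer that the analyst is free to choose between two endpoints, but the three definitions leave little room for that. What remains is that the document calls a case a failure and then scores it as not infested without saying that this is intended. A statistical analysis plan not seen here could add scoring detail, but could not reconcile the two without departing from one of them.

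**Some failures are retained.** Sections 2.3.7, 3.2 and 3.4 would carry forward an infested observation for a case handled as a drop-out. So a reader might infer that every mid-study case becomes a success, and that is not so. The protection is only partial, because withdrawal is not automatic, and it creates the unequal scoring shown above.

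**Complaints may be rare.** Section 1.4 discourages participants from looking for lice, and 1.1 plans no other active assessments. This stands, and it makes the low reporting rates at least as plausible as the high ones. The 45–47% figure needs 40% reporting in control and half that in the active arm; nothing in the protocol supports it as a forecast.

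**The rates may be Day 14 rates.** Section 3.4 quotes 0.7 shortly after tying the parameter to Day 14, and the outcome definition in the earlier studies is not given. This stands and leaves the power effect open.

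**Counting complaints has its own bias.** Day 14 combing is uniform; complaints are not. Household members other than the index case are not combed at Day 0 unless they complain, so an early complaint may be a pre-existing infestation. This stands and is why the fix carries two sensitivity analyses.

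**Conclusion.** The mismatch is real and rests on the protocol's text alone. A confirmed mid-study infestation is a failure in 1.4. In the primary outcome it counts as not infested if the participant is treated, stays and is clear at Day 14, and possibly as infested if the participant drops out.

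The size is unknown. Read as cumulative rates with 80% clearance, the planned figures lose little power at 5–10% equal reporting (about 90% and 88%) and more at higher or unequal reporting. Read as Day 14 rates, they lose none.

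A reader might infer that the rule favours the test shampoo. The documents do not support that. With equal reporting more control cases are available to be erased, so dilution is expected; a bias in favour of the shampoo would need sufficiently more reporting or clearance in its arm, for which there is no evidence either way. Nor do the documents support a claim that the trial is underpowered on this account. The case for change is that the outcome should count the event that the trial sets out to prevent, and count it the same way for everyone.

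**What to change.** In 3.1.2 and both places in 3.4, align the primary outcome with the failure rule in 1.4:
- Count a participant as infested in the household proportion if the study team confirms live lice on complaint at any time after Day 0, or if live lice are found at Day 14. This holds whatever the Day 14 result and whether or not the participant stays in the study.
- State that the index case's scheduled Day 3 and Day 6 checks of the original infestation are not failures in themselves.
- Report the Day-14-only definition as a sensitivity analysis.
- Report a second sensitivity analysis that excludes complaints in the first few days, with the window fixed before unblinding, because these may be infestations already present at Day 0.
- Say in the sample-size text which outcome 0.7 and 0.4 describe.

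The cost is wording: the failure is already to be recorded in the CRF, and participants' treatment is unchanged. The downside is that the outcome takes in some complaint-driven detection, which blinding and the Day-14-only analysis limit.
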